- The average half-life ranged from 3.7 to 5.6 hours for single doses.
- There were no effects of the fed state at 20 and 40 mg doses.
- Following JBT-101 administration at 20-40 mg b.i.d. for 7 days in humans, the only observable plasma metabolite of JBT-101 was a glucuronide metabolite [103], which represented 9% of total JBT-101 present in the plasma.

The safety findings in each completed individual clinical trial can be found in detail in the IB for JBT-101. In summary, key safety findings from the two Phase 1 trials (CT-3-01, CPL7075-100-01) and two Phase 2 trials (CPL7075/02/01/001.1, JBT101-SSc-001) are:

- Maximum Tolerated Dose is 180 mg total daily dose
- No deaths and no serious, severe or unexpected AEs related to JBT-101 occurred in any of the studies
- One of 27 (3.7%) JBT-101-treated subjects in the SSc trial (JBT101-SSc-001) withdrew due to a TEAE of moderate dizziness.
- Mild to moderate AEs consistent with CB1/CB2 agonists occurred at higher doses, especially ≥ 150 mg/day total daily dose
- In pooled safety data, TEAEs that occurred in ≥ 5% of 88 JBT-101-treated subjects who received doses within the estimated therapeutic range of ≤ 60 mg total daily dose were dizziness (n = 10, 11%), dry mouth (n = 5, 5.6%), arthralgias (n = 6, 6.8%), GI disturbances (n = 6, 6.8%) and fatigue (n=9, 10.2%). Note that the majority of subjects with GI complaints (6/6), fatigue (8/9) and arthralgias (6/6) were in the SSc trial and all of these symptoms are common in SSc.
- In pooled safety data of all trials (n = 150 total) and all doses of JBT-101, which included 71 subjects who received JBT-101 at doses higher than the estimated therapeutic range, TEAEs that were observed in two or more subjects ≥ 5% of the time included mild dizziness (21.3%), moderate dizziness (10%), mild somnolence (6%), mild nausea (12%), mild dry mouth (8%), and mild fatigue (5.3%) (Table 27 of the Investigator Brochure for JBT-101). These AEs were consistent with CB1/CB2 agonist class effects and showed a dose-response. Most AEs occurred in the highest frequency in subjects who received ≥ 150 mg total daily dose of JBT-101. Adverse events that were reported in ≥ 5% of placebo-treated subjects were headache (5.7%). There were no AEs or laboratory abnormalities that indicated immunosuppression or an increase in rate of infection.

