- In JBT101-SSc-001, multiple different glucuronide metabolites of JBT-101 were observed in the plasma at < 10% with one glucuronide metabolite present at >10% at all doses. An open-label extension to the JBT101-SSc-001 study is ongoing, with 36 subjects enrolled as of July 2017. All subjects in the open-label extension receive JBT-101 20 mg once or twice per day, for up to 12 months. As of July 2017, total duration of double blind placebo controlled and open-label extension dosing with JBT-101 was median 234 days (range 28, 295 days). All 36 subjects had at least one open-label extension visit ≥ 28 days post baseline. Adverse events (AEs, n = 88) occurred in 28/36 (78%) subjects in the open-label extension. Most AEs were mild (55/88, 62%) or moderate (30/88, 34%) in severity and unrelated to JBT-101 (75/88, 85%). The AEs that occurred in ≥ 10% of subjects (n, % of subjects) were mild fatigue (5, 14%) and mild/moderate upper respiratory tract infection (4, 11%).

Study JBT101-CF-001 is a double-blind, placebo-controlled, randomised Phase 2 study conducted at 21 centres in the US and Europe. JBT-101 was administered at 1 mg once per day or 5 mg once per day for 28 days, escalating to 20 mg once per day or 20 mg twice per

day for an additional 56 days in subjects with cystic fibrosis. Eight-five subjects were dosed with study medication, the last subject has completed the trial, and it is estimated that ~61 subjects received JBT-101 and ~24 subjects received placebo throughout the trial. Safety data is summarized as follows:

- The majority of spontaneously reported adverse events were mild to moderate in JBT-101 treated subjects. The most frequent adverse event reported during JBT-101 treatment was mild dry mouth.
- Four of 61 (6.6%) of JBT-101 subjects withdrew following a TEAE, of which two were considered related to JBT-101 including mild lack of cognitive clarity, and a moderate feeling unmotivated. One of 24 (4.2%) of the placebo subjects withdrew following mild difficulty focusing, mild lack of cognitive clarity
- Triplet ECGs with QT/QTc interval measurements were done throughout the trial and showed no significant changes from baseline and similar findings in subjects who received JBT-101 and placebo.
- Overall, changes from baseline in the ARCI-M were similar in subjects who received JBT-101 and placebo.

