3.1.1 Stratification, Randomization, and Blinding

Eligible subjects will be randomized in a 1:1:1:1 ratio to one of four cohorts: 5 mg JBT-101 b.i.d., 20 mg JBT-101 q.d., 20 mg JBT-101 b.i.d., or placebo (see Section 3.1, *Description of Study Design*, Table 1). Subjects will be stratified by 7-day average of maximum daily pain NRS score ≤ 6 versus > 6 and Fibromyalgia Symptom Scale Score < 13 versus ≥ 13 at Screening.

To maintain the study blind, JBT-101 and placebo capsules and their packaging will be identical. All subjects will receive b.i.d dosing to maintain blinding to treatment assignment. In general, clinical staff, including the investigators, will be blinded to the treatment assignments until completion of the study. In addition, they will not have access to any mechanistic data, and mechanistic laboratory staff will not have access to any clinical results until completion of the study. The success of blinding will be formally tested using a Treatment Satisfaction Survey that asks each study subject and corresponding site investigator to guess the study group assignment for that subject at the end of active treatment and then comparing these responses to what would be expected by chance.

Unblinding must be approved by the study Medical Monitor unless an immediate life threatening condition has developed and the Medical Monitor is not accessible. The site investigator will notify the protocol chair(s) and the DAIT- Statistical and Clinical Coordinating Center (SACCC) of the unblinding event on the next business day. The emergency unblinding will also be reported to the Data and Safety Monitoring Board (DSMB).

A full account of the event will be recorded, including the date and time of the unblinding, the reason for the decision to unblind, and the name of the individual who made the decision and the names of the Medical Monitor and others who were notified. The reasons for unblinding of a participant's treatment will be included in the final study report.

An individual's treatment assignment will be unblinded if the subject experiences a suspected adverse reaction that is serious and unexpected (see Section 7.2.1, *Adverse Event* and Section 7.2.1.1 *Suspected Adverse Reaction* and Section 7.2.2, *Unexpected Adverse Event*) or other protocol-specific event(s) determined by DAIT/NIAID to warrant unblinding.

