5.8.1.1 Procedures for Discontinuation of Protocol-Specified Treatment Requirements

Whenever possible, subjects who have been discontinued from study treatment should complete all scheduled study visits including all exams, procedures, assessments, and tests for the duration of the study. Furthermore, if discontinuation is due to safety concerns, subjects will be given appropriate care under medical supervision beyond the last scheduled study visit, if necessary, until the symptoms of any AE resolve or the subject's condition becomes stable. If the site Principal Investigator (PI) determines that completion of these visits is not clinically appropriate for the subject or if the subject or subject's guardian elects not to complete these visits, the subject will be withdrawn from the study per the guidelines in Section 5.8.2.1, *Procedures for Subject Withdrawal from the Study*.

5.8.2 **Subject Withdrawal from the Study**

When a subject is withdrawn from the study, protocol-specified treatment requirements are discontinued, and study-related visits, exams, procedures, assessments, tests and data collection are terminated. Individual subjects will be withdrawn from the study under the following conditions:

- The subject or subject's guardian withdraws consent
- If the subject elects to participate in any other sort of study or clinical trial (excluding observational registries or cohorts), the subject may be withdrawn at the discretion of the DAIT/NIAID
- Subject non-compliance with treatment regimens or failure to keep appointments

5.8.2.1 **Procedures for Subject Withdrawal from the Study**

All withdrawn subjects will have a follow-up visit after study product is discontinued for final safety monitoring. The timing of the Early Withdrawal Visit in this study is 28 ± 3 days after study product is discontinued. Assessments will be the same for subjects who withdraw before completing all dosing and those who complete all dosing. Subjects who withdraw consent will be asked to complete the Early Withdrawal Visit; however, they will not be required to complete the visit.

Subjects who are withdrawn due to pregnancy will be followed according to the procedures outlined in Section 6.1.9, *Pregnancies*.

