6.1.7 Electrocardiograms and QT/QTc Intervals

Twelve-lead ECGs are to be recorded in triplicate at Screening and Visits 1 (Day 1) and 5 (Day 85). They will be evaluated for medically significant abnormalities and QT/QTc intervals. The QT/QTc intervals will be measured at Visit 1 (Day 1) before administration and between 2.5 and 3.5 hours after administration of study product in the clinic, at the time of maximum JBT-101 concentration in the blood.

The triplet twelve-lead ECGs are to be recorded at least 5 minutes apart, with the subject in a rested supine position for at least 10 minutes. Food and drink should not be consumed by the

subject within the 30 minutes before the ECGs are to be recorded. A central reading center will be used to read all ECGs and determine QT/QTc intervals.

Abnormal ECG findings will be reported as adverse events if they meet grading and reporting criteria (See Section 7.4, *Grading and Attribution of Adverse Events*).

6.1.8 **ARCI-M Questionnaire**

The ARCI-M questionnaire will be completed by subjects at Visits 1 (Day 1), 3 (Day 29), and 5 (Day 85). This is a 12-item yes-no questionnaire developed by the National Institute on Drug Abuse, designed to detect the full range of subjective responses experienced by marijuana users [106]. The ARCI-M questionnaire has been validated by subjects following marijuana smoking. The subject will be asked to fill out the ARCI-M questionnaire prior to other interactions with study staff except for Visit 1 (Day 1). At Visit 1 (Day 1), the ARCI-M questionnaire will be completed at the beginning of the visit, prior to interaction with study staff and between 2.5 and 3.5 hours after administration of study product in the clinic, at the time of maximum JBT-101 concentration in the blood. Evidence of psychotropic effects of the study drug in subjects will be identified by an increase of ≥ 1 in the ARCI-M score assessed longitudinally.

6.1.9 **Pregnancies**

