A. The screening period can be any duration between 7 and 42 days prior to Visit 1 (Day 1), provided the duration is adequate to ensure the subject meets all inclusion and exclusion criteria and drug can be shipped to the site on time for that subject. Screening can take place over more than one visit to the clinic. Screening laboratory tests, other than HIV, hepatitis, or pregnancy testing, can be repeated at the investigator's discretion.

- B. For women of childbearing potential.
- C. Seated (> 5 minutes) blood pressure and pulse.
- D. Will be measured at Visit 1 (Day 1) both before and 2.5 to 3.5 hours after administration of study product in the clinic.
- E. Record within 24 hours after most recent diary entry to prevent reporting of the same data.
- F. ARCI-M will be assessed at the Early Withdrawal Visit if a subject is withdrawn from the study or discontinues the study prior to Visit 6 (Day 113).
- G. At the end of treatment, both the subject and physician will complete a Treatment Satisfaction Survey. If a subject withdrawals from treatment prior to Day 85, the Treatment Satisfaction Survey will be completed at the Early Withdrawal Visit.
- H. Infectious disease screen including HIV antibody, hepatitis B surface antigen, hepatitis C virus (HCV) antibody with HCV RNA (PCR) if antibody positive (unless documented as negative within 12 weeks prior to the Screening visit).

- I. TB testing will be done centrally using a QuantiFERON® blood test. Testing is optional if skin or blood testing was done within 12 months before Visit 1 (Day 1), with documented negative results. See section 6.1.10 *Tuberculosis Screening* for repeat testing options.
- J. For women > 45 and ≤ 55 years of age with no menses for < 2 years.
- K. Complete metabolic panel includes at least glucose, urea nitrogen, creatinine, sodium, potassium, chloride, carbon dioxide, calcium, total protein, albumin, total bilirubin, alkaline phosphatase, aspartate aminotransferase, alanine aminotransferase, and calculated glomerular filtration rate.
- L. Blood and urine tests will be performed prior to study product administration.
- M. Laboratory tests as relevant to the reason for the unscheduled visit.
- N. Pregnancy test at screening can be done through a blood or urine test.
- O. If the subject provides written informed consent, blood samples, including serum, plasma, mRNA, and PBMC culture supernatants, will be stored for future unspecified studies related to JBT-101 or SLE.

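### Subjects who stop early need not give an ARCI-M score or a treatment guess at the stop; both are deferred to a visit 28 ± 3 days after the last dose

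*Protocol*

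**What the plan says.** **ARCI-M.** This is the instrument for safety endpoint 7 (3.2.3). Section 6.1.8 schedules it at Visits 1, 3 and 5. At Visit 1 it is given before the dose and again "between 2.5 and 3.5 hours after administration of study product in the clinic, at the time of maximum JBT-101 concentration in the blood". It is not in the lists for Visit 2 (6.4.2.2) or Visit 4 (6.4.2.4), the minimum list for an unscheduled visit (6.4.4), or the Unscheduled Visit column of Table 3.

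**Blinding survey.** Section 3.1.1 tests blinding by asking subject and site investigator to "guess the study group assignment for that subject at the end of active treatment", and 6.2.4 gives the same timing. Table 3 puts the survey at Visit 5.

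**Early leavers.** Footnote F says "ARCI-M will be assessed at the Early Withdrawal Visit if a subject is withdrawn from the study". Footnote G says "If a subject withdrawals from treatment prior to Day 85, the Treatment Satisfaction Survey will be completed at the Early Withdrawal Visit". Section 6.4.2.7 lists both forms at that visit, and 5.8.2.1 fixes its date: "The timing of the Early Withdrawal Visit in this study is 28 ± 3 days after study product is discontinued".

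**At the stop itself.** Section 6.4.2.7 asks for the procedures of the scheduled visit if the subject leaves at one. Otherwise it asks for a prompt unscheduled visit with evaluations suited to the reason for leaving. It names neither form there.

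**Stopping drug only.** Section 5.8.1.1 keeps subjects who stop drug on all scheduled visits where possible.

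**Analysis.** Section 8.3.3.4 summarises ARCI-M at Visit 1 (before and after the dose), Visit 3 and Visit 5.

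**The concern.** ARCI-M asks about subjective effects of the drug while they are present. A subject who stops because of such effects is the one whose score matters most, yet the form added for that subject is filled in about four weeks later. Section 8.3.3.4 does not list that score among its time points. Visit 6 carries no ARCI-M either, so completers supply no off-drug score to set beside it.

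The blinding test has a similar problem. Completers guess at Visit 5, nominally the day after the last planned dosing day. Early stoppers, some of whom may have been unblinded by side effects, guess about a month after their last dose. Section 3.1.1 compares the responses with chance and does not separate the two kinds of guess.

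The footnotes also disagree on whom they cover. Footnote F is keyed to leaving the study, and footnote G to leaving treatment. For a subject who stops drug and stays in the study, footnote G points to an Early Withdrawal Visit, while 5.8.1.1 keeps that subject on the regular schedule with its survey at Visit 5.

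**Working it through.** **1. Is any drug left at the Early Withdrawal Visit?**
Inputs: 28 ± 3 days (5.8.2.1), and from 1.3.4, "The average half-life ranged from 3.7 to 5.6 hours for single doses".
Half-lives elapsed = days × 24 / half-life.

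| Days after last dose | Half-life 5.6 h | Half-life 3.7 h |
|---|---|---|
| 25 | 600/5.6 = 107.1 | 600/3.7 = 162.2 |
| 28 | 672/5.6 = 120.0 | 672/3.7 = 181.6 |
| 31 | 744/5.6 = 132.9 | 744/3.7 = 201.1 |

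Even in the slowest case the fraction left is 2^(−107.1), about 10^(−32.3). Plasma drug is gone.

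**2. How old is the last scheduled on-drug ARCI-M at the stop?**
Scheduled scores before the end of treatment: Day 1 post-dose and Day 29. Early Withdrawal Visit = stop day + 25 to + 31.

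| Stop day | Last scheduled on-drug score | Age at stop | Early Withdrawal Visit |
|---|---|---|---|
| 14 | Day 1 | 13 days | Days 39–45 |
| 28 | Day 1 | 27 days | Days 53–59 |
| 57 (Visit 4) | Day 29 | 28 days | Days 82–88 |
| 70 | Day 29 | 41 days | Days 95–101 |

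Every dosed subject therefore has at least one scheduled score on drug. What is missing is a required score near the stop.

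**3. The subject who stops drug but stays in the study.**
Under 5.8.1.1 a Day 14 stopper goes on to Visit 5, which is 85 − 14 = 71 days after the last dose. Under footnote G the survey belongs to an Early Withdrawal Visit on Days 39–45. Neither date is the end of active treatment, and the protocol does not say which applies.

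**4. How many subjects?**
*ARCI-M.* In the cystic fibrosis trial (1.3.4), four of 61 subjects on drug withdrew after a TEAE, of which "two were considered related to JBT-101 including mild lack of cognitive clarity, and a moderate feeling unmotivated". One of 24 on placebo withdrew with comparable complaints. If those rates carried over:
- active: 2/61 = 3.3%; × 75 = 2.5 subjects
- placebo: 1/24 = 4.2%; × 25 = 1.0 subject

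That is about 3.5 of 100, with no excess on drug in the source figures.

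*Survey.* Section 8.1 allows the sample to be increased if more than 12% of treated subjects discontinue treatment early. 0.12 × 100 = 12 subjects at that trigger.

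**5. How much would a stop visit recover?**
A visit 48 h after the last dose is 48/5.6 = 8.6 to 48/3.7 = 13.0 half-lives later. At 8.6 half-lives, 2^(−8.6) is about 0.26% of the drug. An ARCI-M given then is also essentially off drug. A treatment guess does not depend on drug still being present.

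**The case against.** A reader might infer that subjects who stop for cannabinoid effects have no on-drug ARCI-M and no treatment guess. The protocol does not support that. Everyone dosed is scheduled for ARCI-M near peak concentration after the first dose, and anyone still dosing at Day 29 has another. A guess is collected, only late. The prompt visit in 6.4.2.7 leaves room for ARCI-M when the reason for leaving is psychotropic, and the list in 6.4.4 is a minimum.

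A reader might also infer that the psychotropic assessment as a whole is biased toward no effect. That goes too far:
- Section 8.3.3.4 reports the count with a rise of 1 point or more after the first dose separately, before drug effects can cause dropout.
- Subjects who stop drug should still attend Visits 3 and 5 where possible, so those counts are not confined to subjects who tolerated it.
- Safety endpoint 6 counts discontinuations due to TEAEs at least possibly related to study product, and 8.3.1 tabulates reasons for discontinuation.
- The cystic fibrosis rates (2/61 on drug, 1/24 on placebo) show no differential.

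How an Early Withdrawal score is tabulated can also properly be left to an SAP.

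All of that stands. It does not answer the timing point. A first-dose score cannot show an effect that emerges later. Scores taken at the site's discretion are not standardised data for a named safety endpoint. A subject who stopped drug and then attends Visit 3 or 5 gives an off-drug score there. No SAP can recover a form that was not collected at the right time, and the mismatch between footnote G, 3.1.1, 6.2.4 and 5.8.1.1 lies within the protocol.

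**Conclusion.** The point holds as a timing defect of modest size. For early stoppers the protocol requires neither form at the stop, except where stopping falls at Visit 3 or 5 (ARCI-M) or Visit 5 (survey). The substitutes are taken 25 to 31 days after the last dose. For ARCI-M this yields an off-drug score with no stated use. For the survey it departs from the timing in 3.1.1 and 6.2.4 and mixes late guesses with completers' end-of-dosing guesses. Footnote G also conflicts with 5.8.1.1.

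The likely reach is a few subjects for ARCI-M, assuming the cystic fibrosis withdrawal rates apply here in a different disease and dosing scheme. For the survey it is about 12 of 100 at the 12% trigger. That figure is a ceiling: it covers discontinuation for any reason and includes subjects who may stay on the regular visits. The documents give no figure for how far a guess changes over four weeks, so the harm to the blinding test cannot be quantified.

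**What to change.** - **Collection.** Require both Treatment Satisfaction Surveys (subject and physician) and ARCI-M at the visit where study product is stopped, whether a scheduled visit or the unscheduled visit in 6.4.2.7. Apply this to subjects who withdraw and to those who stop drug but stay in the study. Record the time of last dose with each form.
- **Fallback.** Keep the survey at the Early Withdrawal Visit only where the stop-visit survey was missed, and flag it as late. Dropping it there altogether would lose the only guess from those subjects.
- **Analysis.** In 8.3.3.4, report the stop-visit ARCI-M with time since last dose, and count it as on-treatment only if the subject was still dosing.
- **Wording.** Reword footnotes F and G so that both say whether they apply to leaving treatment or leaving the study, in agreement with 5.8.1.1.

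The cost is small: two short existing forms at a visit that 6.4.2.7 already calls for on withdrawal, edits to Table 3, and one extra table row. For subjects who stop drug but remain on study, a visit at the stop may have to be arranged. Some stop visits will fall days after the last dose, so the ARCI-M taken there may also be off drug. The main gain is in the blinding survey.

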7 SAFETY MONITORING AND REPORTING

7.1 Overview

This section defines the types of safety data that will be collected under this protocol and outlines the procedures for appropriately collecting, grading, recording, and reporting those data. Adverse events that are classified as serious according to the definition of health authorities must be reported promptly (per Section 7.5.4, *Reporting of Adverse Events to IRBs*) to the DAIT/NIAID. Appropriate notifications will also be made to site principal investigators, Institutional Review Boards (IRBs), and health authorities.

Information in this section complies with ICH Guideline E2A: Clinical Safety Data Management: Definitions and Standards for Expedited Reporting, ICH Guideline E-6: Guideline for Good Clinical Practice, 21CFR Parts 312 and 320, and applies the standards set forth in the National Cancer Institute (NCI), Common Terminology Criteria for Adverse Events (CTCAE), Version 4 : http://ctep.cancer.gov/reporting/ctc.html.

